1.4. Dose Rationale and Risk/Benefits

An SPL oral dose of 25 mg daily has been associated with improvement in mortality and ventricular function in a large, heart failure trial⁵⁰, and a 25 mg daily dose has also been associated with improvement in ventricular structure and function in mild to moderate CKD. Doses tested in ESRD have ranged from 25 mg 3x/week to 50 mg 2x/day. Although, a 25 mg daily dose has been the most frequently tested, and appears to be well-tolerated and associated with a minimal incidence of serious hyperkalemia as detailed in Section 1.3 and Table 1, the optimal dose in terms of safety and efficacy in the ESRD population remains uncertain. To our knowledge, no study to date has compared the relative safety, efficacy, or tolerability of multiple doses with each other or with placebo within the structure of a single trial. Thus, in order to generate comparative information on safety, efficacy and tolerability, the current study will compare 3 doses of SPL, representing a low dose (12.5 mg/day), a medium dose (25 mg/day) and a high dose (50 mg/day), with placebo therapy. Spironolactone will be administered once per day. On days in which dialysis is performed the drug will be taken post-dialysis to minimize effects of dialysis on drug metabolism. In addition to spanning a range from low to medium to high dose, the targeted doses of SPL are consistent with available tablet sizes and standard clinically utilized/approved doses for the FDA-labeled indications. Although additional doses could be tested, it is uncertain whether significantly greater knowledge would be generated through the addition of medium-high dose (e.g. 37.5 mg/day) compared with the current plan to test low, medium and high dosing strategies. Conversely, addition of an ultra-high dose group (e.g. >50 mg/day) is more likely to be associated with a high rate of adverse events necessitating drug discontinuation. Additional dosing arms also have the disadvantage of increased logistical complexity. Furthermore, in the absence of an increase in overall sample size, a smaller cohort size in each dose group could have the undesired effect of limiting power to detect differences in safety or efficacy across doses. The increase in the overall sample size required to increase power across 4 or more active dose groups would increase the costs, recruitment challenges, and probably the duration of the trial.

1.4.1. Risks

Risks of SPL include hyperkalemia, hypotension and intra-dialytic hypotensive symptoms. Other potential side effects include gynecomastia and gastrointestinal symptoms. Of particular concern in trials of SPL in patients with CKD is the risk of hyperkalemia and the potential for hyperkalemia-associated arrhythmias. Although the effects of SPL on potassium excretion are important, it is noteworthy that extracorporeal (dialytic) clearance, rather than renal or colonic clearance, provides the majority of potassium excretion in dialysis-dependent ESRD. This extracorporeal clearance should not be impaired by SPL therapy.

In the current trial, risks of hyperkalemia will be reduced through close monitoring of serum potassium concentrations through scheduled study-specific safety labs, and through standard clinical practice at the treating dialysis unit (monthly to bi-monthly in individuals with normal serum potassium, more frequently in individuals with hyperkalemia or hypokalemia). Manipulation of dietary intake of potassium, eliminating, when medically acceptable, concomitant use of medications with hyperkalemic effects, and adjustment of dialysate

potassium will also be used as additional safety measures (see **Section 6.8**). The use of low potassium dialysate is currently considered by many clinicians to be an appropriate approach for treating hyperkalemia, and dialysate potassium concentration may be altered according to standard practice of the treating clinicians throughout the course of the study. However, the study protocol will not mandate or recommend prophylactic changes to the dialysate prescription and calls for lowering dialysate potassium only as a second-line response to significant hyperkalemia after other measures fail to resolve hyperkalemia. The relative risks of arrhythmic death from hypokalemia, hyperkalemia and low dialysate potassium levels in hemodialysis patients is an active area of inquiry and uncertainty and further research into the best approach is warranted⁶⁸⁻⁷⁰. In the absence of definitive data on the optimal approach to dialytic management of serum potassium concentration, evaluation of the relative risks and benefits of SPL therapy within the context of standard clinical approaches to dialysate potassium prescription will increase the understanding of the true risks and benefits of SPL therapy within the context of standard clinical approaches to hemodialysis in the United States.

Given these uncertainties and equipoise regarding the ideal serum potassium concentration and ideal dialysate potassium in chronic hemodialysis patients, changes in dialysate potassium concentration will be recommended only as a secondary means of controlling serum potassium to be utilized only in the context of significant hyperkalemia. Use of 1 mEq/L potassium dialysate will be recommended only as a temporizing measure of last resort. The proportion of treatments requiring use of 1 mEq/L dialysate will be monitored as a secondary safety endpoint and compared across treatment groups.

1.4.2. Benefits

Benefits of SPL therapy in the dialysis population remain unproven at this time. Hypothesized benefits of SPL therapy include improved blood pressure control, improvement in cardiovascular function and structure, and a decrease in arrhythmias.

2. Study Objectives

The primary objective of this study is to characterize the safety and tolerability of multiple doses of chronic SPL therapy compared with placebo in maintenance hemodialysis patients and to assess the feasibility of conducting a full-scale, mortality-powered trial of SPL. The effects of SPL compared with placebo on multiple cardiovascular efficacy parameters will also be analyzed. The primary efficacy parameter will be the change in the E' measurement on tissue Doppler echocardiography (TDI) as an index of diastolic function and a surrogate for myocardial fibrosis. Secondary cardiac parameters of interest that will be studied in the overall population or in sub-studies include heart rate variability, circulating markers of fibrosis, and coronary flow reserve (CFR) as an index of microvascular function. These parameters are designed to broaden insight into the potential effects of SPL on cardiac structure and function in individuals with dialysis-dependent ESRD and to assess the feasibility of conducting a full-scale, mortality-powered trial.

2.1. Primary Objectives

Safety

- To evaluate the safety of chronic spironolactone therapy in individuals with ESRD on HD.
 - Safety events will include the following:
 - Potassium level >6.5 mEq/L
 - Serious hypotension is defined as hypotension requiring hospitalization or treatment in an emergency room and not attributable to overt sepsis, acute myocardial infarction, or other cardiovascular event (e.g. aortic dissection)
 - Serious hyperkalemia defined as hyperkalemia requiring hospitalization, emergency/unscheduled dialysis, or emergency/unscheduled resin therapy
 - The combined incidence of potassium level >6.5 mEq/L or serious hyperkalemia defined as hyperkalemia requiring hospitalization, emergency/unscheduled dialysis, or emergency/unscheduled resin therapy
 - Treatment-emergent events defined as the combined incidence of death, myocardial infarction, stroke, hospitalizations, potassium level >6.5 mEq/L, serious hyperkalemia defined as hyperkalemia requiring hospitalization, emergency/unscheduled dialysis, or emergency/unscheduled resin therapy, and serious hypotension defined as hypotension requiring hospitalization or treatment in an emergency room and not attributable to overt sepsis, acute myocardial infarction, or other cardiovascular event
 - The individual components of the treatment-emergent endpoint
 - Cardiovascular death
 - Hyperkalemia requiring adjustment in dialysate potassium concentration, or discontinuation of study medication
 - Proportion of dialysis sessions utilizing 1 mEq/L potassium dialysis solution bath
 - Within-patient variability in serum potassium concentration
 - Symptomatic inter- or intra-dialytic hypotension

Tolerability

- To evaluate the tolerability of chronic spironolactone therapy in individuals with ESRD treated with hemodialysis
 - Tolerability events will include reduction in dose of study medication during the course of the treatment period or discontinuation of study drug

Efficacy

- To test the hypothesis that chronic blockade of aldosterone with SPL improves diastolic function in individuals with ESRD on HD. The change in E' on TDI echocardiography of the left ventricle from baseline to end of study will be used in the primary endpoint assessment of diastolic function.

Feasibility

- To assess feasibility of conducting a full-scale mortality-powered trial.
 - Feasibility will be assessed based on recruitment rate and dropout rates.

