3.2. Study Endpoints

3.2.1. Primary Endpoints

Safety

The primary safety endpoints are:

- 1) The incidence of serum potassium >6.5 mEq/L
- 2) The incidence of serious hypotension defined as hypotension requiring hospitalization or treatment in an emergency room and not attributable to overt sepsis, acute myocardial infarction, or other cardiovascular event (e.g. aortic dissection).

Tolerability

Tolerability will be assessed on the basis of whether participants can continue the assigned dose throughout the entire treatment period. Any reduction in dose of study medication will be considered a failure of primary tolerability.

Efficacy

The primary efficacy parameters will be measured between baseline and 36 weeks: Change in mitral annular E' velocity will be measured using Tissue Doppler Index (TDI) echocardiography of the left ventricle as a measure of diastolic function and as surrogate measure of left ventricular fibrosis.

E' has been chosen to be the primary echocardiographic endpoint because the intra-observer coefficient of variation is low⁷¹ and multiple studies demonstrate a high correlation with myocardial fibrosis⁷²⁻⁷⁴, a primary biologic endpoint of interest. E', for example, parallels the accumulation of myocardial collagen and fibrosis in the senescence prone mouse⁷⁵, and correlates with endomyocardial fibrosis after human cardiac transplant⁷⁶ as well as the presence of late gadolinium enhancement⁷⁷ – a highly-validated measure of myocardial scar – across multiple disease states. Furthermore, abnormalities in TDI have been strongly linked to mortality in multiple disease states⁷⁸⁻⁸⁰ demonstrating that TDI is a clinically relevant measure. In addition, ESRD-specific studies show that E' is highly correlated with LV mass and other indices of diastolic function, and that changes in E' predict mortality^{34, 81}.

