4.4.2. Early Termination of Study Medication

Study medication will be discontinued by the research team in the following circumstances because of the potential for compromising patient safety:

- Allergy to or documented intolerance of study medications
- Poor adherence with dialysis schedule compromising ability to follow serum potassium on a monthly basis
- Organ transplantation
- Change to a different dialysis modality
- Initiation of digoxin therapy
- Transfer to a non-participating dialysis unit

If study medication is discontinued study visits and procedures will continue unless the participant withdraws consent for follow-up.

5. Study Drug

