5.6. Concomitant Therapy

Medication use (both oral and intravenous) will be collected at baseline and throughout the course of the study. Digoxin use, dual ACE inhibitor/ARB therapy and non-selective beta blocker use are exclusion criteria. If these medications are initiated during follow-up the treating clinician will be contacted by the research team. For digoxin or dual ACEI/ARB use, if the prohibited drug cannot be discontinued, study medication will be withdrawn and participants will continue to be followed. For non-selective beta blocker use, it is anticipated that the treating clinician will be comfortable substituting a selective beta blocker but if not, study drug will be discontinued and the participant will continue to be followed.

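### Sections 2.1 and 3.2.1 disagree on whether stopping study drug is a tolerability failure, and under 2.1 stops imposed for transplant, modality change or unit transfer would count as intolerance

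*Combined protocol and SAP*

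**What the plan says.** Section 2.1 (Tolerability) states: "Tolerability events will include reduction in dose of study medication during the course of the treatment period or discontinuation of study drug". It sets no limit by reason.

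Section 3.2.1 (Tolerability) puts it differently: "Tolerability will be assessed on the basis of whether participants can continue the assigned dose throughout the entire treatment period". Its only explicit failure rule is "Any reduction in dose of study medication will be considered a failure of primary tolerability"; discontinuation is not named there. The Study Summary gives a third description and lists tolerability as treatment adherence.

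Section 4.4.2 introduces a list of mandatory stops: "Study medication will be discontinued by the research team in the following circumstances because of the potential for compromising patient safety". Documented intolerance is one entry. Separate entries include "Organ transplantation", "Change to a different dialysis modality" and "Transfer to a non-participating dialysis unit", as well as poor adherence to the dialysis schedule and the start of digoxin. Section 5.6 adds, for digoxin or dual ACEI/ARB use, "if the prohibited drug cannot be discontinued, study medication will be withdrawn", with a similar conditional rule for non-selective beta blockers.

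Both 4.4.2 and 5.6 keep these participants in follow-up, and 7.3 analyses everyone randomized. Section 7 specifies no tolerability analysis, no coding of reasons and no censoring or competing-event rule. Exclusion criterion (m) in 4.2 removes patients whose transplant, change to peritoneal dialysis or unit transfer is anticipated within 9 months.

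**The concern.** Tolerability is a primary objective, and the background section says the trial should help choose a dose for larger studies. Under 2.1, a participant who takes 50 mg without difficulty and moves to a non-participating unit at week 20 is a tolerability event, the same as one stopped for hyperkalemia. Such stops say little about how spironolactone is tolerated and can occur in any arm, placebo included. Counting them raises the failure rate everywhere and makes the arms look more alike.

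The failure sentence of 3.2.1 does not settle the matter. Taken alone, it would miss a participant whose drug is stopped outright with no prior reduction, as 6.9 provides at a potassium of 7.0 mEq/L or more and 6.10 for unexplained rash. Two analysts could therefore produce different primary tolerability rates from the same data.

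**Working it through.** **Plan's own figure.** The plan gives no rate, power or sample size for tolerability, so there is nothing to reproduce for this endpoint. The only binary power statement (7.1) is 80% for hyperkalemia at 5% v 22% with 125 participants. For 50 v 75 at two-sided 0.05 (sidedness assumed), exact enumeration of the uncorrected chi-square test gives 81%, and a pooled normal approximation gives 77%. Those rates are borrowed below only as an illustration.

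**Inputs.**
- Placebo 50, spironolactone 3 × 25 = 75 (7.1).
- True intolerance p: 5% placebo, 22% pooled spironolactone (borrowed).
- Imposed-stop probability u: not in the documents. Values of 2%, 5% and 10% are assumed, equal in all arms and independent of intolerance.

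**Formulas.**
- Observed failure: q = 1 − (1 − p)(1 − u).
- Risk difference: (1 − u)(p₂ − p₁), so it shrinks by the factor 1 − u.
- Risk ratio: q₂/q₁, which moves toward 1 as u rises.

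At u = 10%:
- placebo 1 − 0.95 × 0.90 = 14.5%;
- spironolactone 1 − 0.78 × 0.90 = 29.8%;
- ratio 29.8/14.5 = 2.1;
- difference 0.90 × 17.0 = 15.3 points.

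**Results, placebo 50 v pooled spironolactone 75.** Power is by exact enumeration. The last column leaves out participants with an imposed stop, as a simple stand-in for censoring (49 v 74, 48 v 71 and 45 v 68 after rounding).

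| u | Observed failure | Risk ratio | Risk difference (points) | Power, all stops counted | Power, imposed stops left out |
|---|---|---|---|---|---|
| 0 | 5.0 v 22.0% | 4.4 | 17.0 | 81% | 81% |
| 2% | 6.9 v 23.6% | 3.4 | 16.7 | 74% | 80% |
| 5% | 9.8 v 25.9% | 2.7 | 16.15 | 66% | 77% |
| 10% | 14.5 v 29.8% | 2.1 | 15.3 | 53% | 76% |

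The share of placebo failures that are not intolerance is (q₁ − p₁)/q₁. At u = 2% it is 1.9/6.9, or 28%; at u = 10% it is 9.5/14.5, or 66%.

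**One dose v placebo (25 v 50).** By the normal approximation, power is 60% with no imposed stops. At u = 10% it is 36% with all stops counted and 56% with imposed stops left out.

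**Other rates.** With 10% v 30% true intolerance and u = 10%, the ratio falls from 3.0 to 37.0/19.0 = 1.9.

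**The case against.** **Wording.** A reader might infer that the plan unambiguously counts every discontinuation as a primary failure. It does not. That rule stands in 2.1, while 3.2.1 names only dose reduction and asks about ability to continue. The firm finding is that the two sections differ and neither separates reasons for stopping.

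**Dropout.** A reader might also infer that these stops are already measured under feasibility. Section 6.6.1 says that participants who only stop medication are not early withdrawals, so a drug stop is not dropout.

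**Prohibited drugs.** Not every start of a prohibited drug ends study treatment. Under 5.6 the treating clinician is contacted first, and study drug stops only if the other drug cannot be discontinued or replaced. (For digoxin, 4.4.2 lists initiation without that condition; the two passages must be reconciled.) Nor are such stops clearly unrelated to treatment. Antihypertensive prescribing can depend on blood pressure, which spironolactone may change, so censoring them could bias the comparison. This objection stands and limits which stops should be set apart.

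**Size.** The stop rate has no source in the documents, and criterion (m) should keep it low. Section 7.1 disclaims formal critical regions and no tolerability test is planned, so the power figures describe loss of information, not failure of a planned test. The risk difference moves little.

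**Estimand.** All-cause discontinuation is a legitimate, adjudication-free measure of persistence and useful for planning a mortality trial. It answers a different question from intolerance, and the plan does not say which it wants.

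**Conclusion.** The point holds in limited form. Sections 2.1 and 3.2.1 give different failure rules, and under 2.1 stops imposed for transplantation, modality change or unit transfer are scored as intolerance on a primary endpoint. If such stops are unrelated to arm, failure rates rise everywhere and the comparison moves toward the null; that direction follows from the formula.

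The size is not known. With the borrowed 5% v 22% rates, the avoidable power loss is about 6 points at 2% stops (74 v 80%), 11 at 5% (66 v 77%) and 23 at 10% (53 v 76%). It would be wrong to read the whole fall from 81% to 53% as recoverable, because leaving these participants out also costs information. The main harm is to the reading of tolerability rates and ratios by dose, which are the main product of a pilot.

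**What to change.** Change the endpoint definition only:

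- Make 2.1, 3.2.1 and the Study Summary agree.
- Define primary tolerability failure as any dose reduction or discontinuation, except a discontinuation whose reason, coded before unblinding, is transplantation, modality change or unit transfer.
- Treat those three stops, and death, as censoring or competing events, and state which in section 7.
- Keep stops for prohibited drugs and for poor dialysis adherence as failures, in the primary definition or in a sensitivity analysis, because they may depend on treatment.
- Report all-cause discontinuation with reasons by arm alongside.

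Cost: rewording three places and adding a short analysis paragraph. The documents do not describe a field recording the reason for each stop, so one must be confirmed or added. Some coding judgement is needed, contained by blinding and by the all-cause report. Slightly fewer participants contribute full tolerability follow-up. No stopping or dosing rule changes.

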2.2. Secondary Objectives

Secondary objectives are designed to expand understanding of cardiovascular structure and function and their association with SPL therapy in ESRD by analysis of the following parameters:

- Change between baseline and 36 weeks in left ventricular mass index (LVMI)
- Change between baseline and 36 weeks in ejection fraction
- Change between baseline and 36 weeks in myocardial strain and strain rate
- Change between baseline and 36 weeks in circulating indices of tissue fibrosis such as procollagen type I carboxy-terminal peptide (PICP), galectin-3, soluble ST2, GDF-15
- Change between baseline and 36 weeks in circulating indices of systemic inflammation such as CRP, IL-1, IL-2, IL-6, IL-10, IL-18, TNF-alpha, albumin, sVCAM-1, leptin, adiponectin
- Change between baseline and 36 weeks in circulating indices of oxidative stress such as F2 isoprostanes and isofurans
- Change between baseline and 36 weeks in coronary flow reserve
- Association between change in coronary flow reserve (CFR) and change in E'
- Heart rate variability
- Arrhythmia

3. Study Design

3.1. General Design

This is a randomized, placebo-controlled 4-arm trial that will compare placebo with 3 doses of SPL. Participants will be randomized in a 2:1:1:1 fashion to placebo or SPL, with equal proportions randomized to each of 3 SPL doses: 12.5, 25 or 50 mg once daily. As shown in **Figure 1**, the study will be conducted in 2 phases – a dose escalation phase and a treatment phase.

All participants randomized to SPL will initiate treatment at 12.5 mg daily. Participants will be evaluated weekly for tolerability, hypotension and hyperkalemia. At 2 weeks, if the initial dose has been tolerated, participants randomized to the 25 or 50 mg SPL arm will increase the dose to 25 mg for 2 weeks with weekly evaluation for tolerability, hypotension and hyperkalemia. Participants randomized to 12.5 mg SPL or placebo arm will continue on the same dose with weekly evaluation for tolerability, hypotension and hyperkalemia.

[figure not shown]
At 4 weeks, participants randomized to the 50 mg SPL arm will increase the dose to 50 mg if the 25 mg dose was tolerated with weekly evaluations for tolerability, hypotension and hyperkalemia.

until 6 weeks. Participants randomized to 12.5 mg, 25 mg, or placebo will continue on the same dose with weekly evaluation for tolerability, hypotension and hyperkalemia until 6 weeks.

In order to maintain the blind, during the dose escalation phase all study participants, regardless of randomized assignment, will receive new study drug kits every 2 weeks and will be evaluated weekly.

At the end of the dose escalation phase, participants will continue treatment based on the randomized dose assignment for an additional 30 weeks (treatment phase) such that the total duration of study medication is 36 weeks. As described in **Sections 6.8 and 6.9**, the dose of SPL or placebo will be decreased during the dose-escalation and follow-up phases for hypotension, hyperkalemia or other dose limiting side-effects.

Figure 1. Study Design

